4.0 Study Endpoints

Study end points include: Successful study completions, Consent withdrawals, PI terminations, Lost contact with the patient, and unexpected adverse events.

5.0 Inclusion and Exclusion Criteria/ Study Population

- Eligible caregiver/child dyads will be identified through the staff at the MUSC Pediatric Sickle Cell Clinic. After receiving permission to approach, PI or PC will

screen the potential participants against the inclusion and exclusion criteria. Screening will be documented in REDCap.

Inclusion Criteria

- Children ages 0 – 7 years and parent or primary caregiver 18 years of age or older
- Child with sickle cell disease, as reported by clinician at the MUSC Pediatric Sickle Cell Clinic

Exclusion Criteria

- Parent/caregiver with cognitive disability or delay that precludes ability to participate
- Lack of access to Wi-Fi

Inclusion of Women and Minorities

Both women and minorities will be included in the proposed study. Women are more often than men reported to be the primary caregiver of children with chronic conditions and approximately 66% of caregivers of adults with chronic illness are women. Therefore, it is anticipated that more women will be recruited as participants than men. In addition, SCD occurs almost exclusively in African Americans; therefore, it is anticipated that all or nearly all of the caregiver participants will be African American.

Inclusion of Children

Children ages 0-7 years will be included as part of the child/caregiver dyad. Proxy data will be collected on children younger than 5 years, and older children (ages 5-7 years) without developmental delay will be invited to complete surveys and participate in key informant interviews with the caregiver.

6.0 Number of Subjects

- N=60 – 30 caregivers of 30 children (0-7 years) with SCD will be recruited.

7.0 Setting

- The intervention will be used by the participants in their community environments. Study visits will occur at MUSC Sickle Cell Unit and via telephone to the participant's home.

8.0 Recruitment Methods

- Parents/caregivers who participated in Phase I of the study and agreed to be re-contacted for future research will be contacted and invited to participate.
- For other potential participants, the MUSC Pediatric Sickle Cell Clinic staff will be given the inclusion/exclusion criteria and will be asked to identify eligible participants in the clinic. When potentially eligible participants attend an appointment at the clinic, the clinician/staff will approach the parent/caregiver, briefly introduce the study through an IRB approved study letter, and if interested ask if the researchers can speak with the parent/caregiver to offer additional information. For parents/caregivers who

agree, the PI or PC will provide an overview of the study either by phone or face-to-face in the clinic and conduct eligibility screening. Eligible and interested parents/caregivers will proceed to the informed consent interview.

- Additionally, for the purposes of this study and in direct alignment with the mission of the CON P20 Symptom Self-Management Center, we will employ the use of MUSC Bioinformatics Center (BMIC) core services to identify and recruit patients across the MUSC Enterprise that meet the study inclusion/exclusion criteria and that have granted authorized research contact permission in MyChart through the electronic ‘opt in’ EPIC designation. Once these potentially eligible patients are identified, we will then contact them by telephone using a script to determine if they are interested in study participation
- Flyers will be posted in the waiting room and patient rooms at the MUSC Sickle Cell Clinic. The flyers will include the PI’s contact information; interested parents/caregivers who call the PI will be screened for eligibility.

9.0 Consent Process

Since research will be conducted with caregiver/child dyads and no research will be conducted without the caregiver present, consent will be obtained from the parent/caregiver for both him/herself and the child participant (0-7 years). In this study, we will employ the use of two informed consenting strategies (In-person meeting and electronically through REDCap e-Consent) so as to increase the reach of the study and to promote the generalizability of findings.

In-person informed consent will occur in the comfort and safety of a private clinic room at the MUSC Sickle Cell Unit prior to any screening procedures being conducted and/or data collection. Potential participants will be given the informed consent document to read and review in advance, and/or may have it read to them by the researchers if they prefer. After reviewing the Consent document, both caregiver and child will be given the opportunity to ask any questions about the study that they may have, and will be requested to demonstrate what is expected from them should they enroll in the study through a questioning of their understanding of study procedures and risks. Prior to consenting, all questions will be resolved to the caregiver and child's satisfaction. If a participant does not appear to understand the information contained within the Consent document, the study coordinator will review the consent document again with the participant. If after this second review, the subject does not demonstrate an understanding, they will not be enrolled in the study. Only participants, with no diagnosed or observed cognitive impairment, will be consented and enrolled into the study.

Electronic or e-Consenting will be performed on eligible families that want to participate in the study but are unwilling for whatever reason and/or unable to come to MUSC for a face-to-face informed consent meeting. Families identified through the study recruitment processes that fall into this category will already have spoken with the researchers by telephone, have been introduced to the study and its demands, as well as had their initial questions answered. After speaking with the researchers, families that are further interested in study participation will be asked to provide an email address at which they will receive a REDCap survey link containing a scanned image of the currently approved Informed Consent document (developed from the MUSC REDCap e-consent template). Families will be able to take as much time as they like to read the consent document together in the comfort and privacy of their own home or at a place and time of their choosing. They will be provided with the telephone and email contact details in the survey instruction header for the researchers, should they have any questions before

providing their consent by adding their respective signatures to the form and submitting it. Prior to providing their physical e-consent, the researchers will coordinate with these families; so as to be on the telephone and be available to further answer any questions that they may have during the e-consent process. Should a participant have any questions or concerns about the study, the researchers will address these issues to the best of their abilities and knowledge. Upon submitting the e-consent, a REDCap trigger will immediately notify the researchers, who will then provide their countersignature to the document.

The consent form will meet the requirements of the Code of Federal Regulations and the MUSC Institutional Review Board; and, include the following elements:

1. The purpose, nature, and objectives, potential risks and benefits of the intended study.
2. The length of study and the likely follow-up required.
3. The name and a contact of the investigator(s) responsible for the protocol.
4. The right of the participant to accept or refuse study interactions and to withdraw from participation at any time.

The HIPPA authorization process will be conducted sequentially with the family in the same manner by the researchers. Participants will be able to download a copy of their executed informed e-consent/HIPAA authorization forms directly to their own computer, or have copies emailed to them. They will also be given the option to have a copy of their executed e-forms mailed to them should they elect to do so. A copy of the executed e-consent/HIPAA authorization forms will also be stored in the participant's electronic case record for monitoring and audit purposes.

10.0 Study Design / Methods

The mHealth SCD management intervention will be delivered via an app on the caregiver's mobile device over a 12-week period. This multi-component, web-based app consists of 1.) continuous access to directed educational resources on the SCD process, treatment, home management strategies, symptom prevention and management strategies; 2.) a series of pages in the app that allow for tracking and monitoring symptoms; and 3.) child/caregiver – provider communication. The educational component is based on patient-centered materials that have been developed and tested by authoritative sources. In the app, educational materials are organized by user age (for individuals with SCD) or role for parents/caregivers. Citations are provided and links to the sources are included. The symptom tracking and monitoring component consists of a customizable avatar on which the user can record the location, severity, and characteristics of pain. Users can record other concurrent or associated symptoms (such as fatigue) and can view a graph with the pain history. This portion of the app also includes a health history page on which users can document important clinical information, such as sickle cell type, last sickle cell crisis hospitalization, medications, and allergies. The child/caregiver – provider communication component consists of the ability for the child/caregiver to send a secure message to providers within the app to communicate pain and other symptoms. Providers will have the capability to securely send a reply within the app. In addition, children/caregivers can choose to receive a daily "support" message that will be automatically sent from a list of possible messages. All communication is encrypted and sent securely within the app via a portal. Two to three providers at the MUSC Sickle Cell Clinic will participate as the designated providers in the study.

To determine feasibility, we will apply the RE-AIM framework to assess the Reach, Efficacy, Adoption, Implementation, and Maintenance of the intervention with 30 children/caregiver dyads.¹⁸ The domains are further explicated in Table 2. The intervention will be loaded onto the

caregivers' tablet or smartphone (Apple or Android); participants without a device will be provided one for the duration of the study. The PI or PC will deliver detailed verbal instructions to caregivers on the use of the device and the intervention. Caregivers will also receive written instructions and a contact number for technical assistance if needed. Baseline measures (Table 2) will be collected during the same meeting. Caregivers will retain the devices and will participate in the intervention over a 12 week-period. At the end of the 12-week period, the PI will conduct a post-intervention meeting with each individual caregiver participant during which data will be collected. Caregivers will also be asked to return the mobile device at the end of the study. The PI will meet with the study provider weekly during the intervention.

Retention: To improve retention, IRB-approved personnel will contact enrolled participants at 3-week intervals between data collection points. The timeline for these points of contact are at the following weeks post baseline data collection: weeks 3, 9, 15, 18, and 21. The purpose is to maintain contact with enrolled participants, not data collection. Correspondence will be logged in REDCap. Contact will take place via text message, using the number(s) provided to study personnel upon enrollment. Examples of messages are provided in an uploaded attachment.

Post-intervention interviews. At the end of the 12-week study, all 30 caregivers will be asked if they would like to participate in a 3-month post-intervention key informant interviews with the PI to obtain more in-depth data on accessibility, usability, and adherence to intervention; however, only 15 will be chosen to participate. This subset will be selected randomly by computer. Dyads have a 50-50 chance of being randomly selected if all dyads express interest. Semi-structured interviews will be conducted using a qualitative descriptive approach,¹⁷ will last approximately 45-60 minutes, and will be conducted according to an interview guide with open-ended questions and prompts. These interviews will be audio recorded for later nVivo qualitative data analysis. Selected caregivers will be given the option of having the interview conducted in-person in a private room at MUSC or by telephone in the comfort and safety of their own home.

Reimbursement for dyads will be a \$50 gift card provided at each of the 4 data collection points, with dyads in key informant interviews receiving an additional \$40 gift card. All payments will be given to the caregiver.

Measures. Older children (5-7 years) and their caregivers will complete age-appropriate self-report and proxy assessments at baseline, mid-intervention (6 weeks), post-intervention (12 weeks), and 3 months post-intervention as previously described. Self-report and proxy assessments will be collected during meetings between the PI or PC and the participant. Depending on participants' preference and availability visit 2, 3 and 4 surveys will be completed either by phone or electronically via REDCap survey or by paper and pencil. All data will be recorded in REDCap by the PC.

11.0 Specimen Collection and Banking

Not applicable

12.0 Data Management

Sample size considerations

The purpose of this study is to establish feasibility of implementing the integrated intervention obtain estimates of variability for the primary outcome measures and obtain preliminary indicators of effectiveness of the intervention rather than to confirm or refute hypotheses.

Therefore, sample size considerations focus on precision of estimates. For this feasibility study, we project that we will be able to recruit 30 child/caregiver dyads. With such a sample we will be able to estimate outcome proportions for feasibility measures including recruitment and drop-out with precision ± 0.11 to ± 0.16 for values of the true proportion ranging from 0.10 to 0.30 (or correspondingly, from 0.70 to 0.90). Assuming a drop-out rate of up to 30%, 95% confidence limits can be estimated for impact measures, such as change from pre-to-post in quality of life for child and caregiver with a precision ranging from ± 0.43 to ± 1.35 corresponding to estimated standard deviations for change in quality of life scores ranging from 0.5 to 5.0 SD units.

Demographic and clinical variables obtained at baseline will be described via measures of central tendency (mean, median), variability and frequency distributions as appropriate. Additionally, demographic and clinical characteristics for those who adhered to the study protocol (study completers) versus those who did not adhere (non-adherers and drop-outs) will be compared to better describe the population for this study. For continuous quality of life measures for the child and caregiver the difference between pre and post intervention measurements will be estimated via 95% confidence intervals. To assess preliminary intervention effects, we will conduct repeated measures ANCOVA with symptom (pain) severity and type obtained daily as dependent variable in individual models adjusting for “dose” defined as number of times education module was accessed and total time spent in education modules.

Post-intervention qualitative analyses (Aim 2): Data collected from post-intervention key informant interviews will be analyzed using directed content analysis¹⁹ and nVivo qualitative data analysis software version 11.²⁰ Consistent with the directed content analysis approach, initial coding categories are identified according to the guiding theoretical model, and for this study, will reflect the RE-AIM domains.

Data sharing with the NINR/NIH: As a condition of this National Institutes of Nursing Research (NINR) award, de-identified patient data will be shared by the researchers with the NINR and stored electronically on an NIH password protected secure server (<https://cdrns.nih.gov/>). The purpose of sharing this information is to build a NINR repository of data using Common Data Elements (CDE) for future research purposes among the general scientific community and for public health benefit. Patients will be allocated a random identifier through the NIH supported GUID Tool. The GUID Tool (<https://cdrns.nih.gov/node/39>) is a customized software application that generates a Global Unique Identifier for each study participant. The GUID is a subject ID that allows researchers to share data specific to a study participant without exposing personally identifiable information (PII). The GUID is made up of random alpha-numeric characters and is NOT generated from PII/PHI. As such, it has been approved by the NIH Office of General Counsel. GUID Generation complies with HIPPA regulations for the protection of PII/PHI. Patients are made aware of this data sharing agreement with the NINR/NIH in the study's Informed Consent document.

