During Phase I of this study, using an iterative design process and guided caregiver, child and clinician feedback, we developed and refined the intervention by conducting user focus groups and pilot testing the app among a target population of end-users. Specific tasks accomplished during this Phase I, included developing and incorporating age specific language into the app, refining the user graphical user interface, developing and integrating the provider communication component to include clinically relevant disease specific symptoms, and build-out of the clinician's patient portal – where individual patient's data can be accessed for summary viewing. Now, in Phase II, we aim to deploy the intervention in a real-world setting.

Children (5-7) with SCD and their caregivers will complete self-report and proxy assessments as described in Table below; data will be recorded in REDCap by the PI or project coordinator

Major tasks and domains	Measures/instruments/questions and Cronbach's alpha ()	Data sources and time points
Demographics/clinical characteristics	Age, child age, health history, race/ethnicity, medications, health care utilization, rural/urban residence, insurance, caregiver demographics, family characteristics	Caregiver interview; baseline
Reach: Sample Recruitment	Monitoring of sample representativeness; types of recruitment activities; rates of recruitment; % eligible, consented, provided with informational session	Recruitment tracking forms; quality checks by PI; weekly meetings with mentor, clinic staff, and research team
Efficacy: Child (by proxy): Pain Fatigue Quality of life Caregiver: Fatigue Emotional distress: anxiety Emotional distress: depressive symptoms	PROMIS Parent Proxy: Pain Interference* ^{21,22} (age 5 and older) PedsQL with Sickle Cell Disease Module (proxy = 0.97) ²³ (age 2 and older) PedsQL Multidimensional Fatigue Scale in Sickle Cell Disease (proxy = 0.95) ²⁴ (age 2 and older) PROMIS Fatigue SF (>0.9) ²⁵	Review and content analysis of transcriptions of text messages; review and content analysis of recorded teleconferences; tracking forms; fidelity checklist; transmissions from web-based application to nurse; post-intervention interviews; weekly

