Measures of self-management behaviors: Monitoring and tracking symptoms Attending clinic appointments Administering home medications and treatments	PROMIS Emotional Distress: Anxiety (0.97) ²⁶ PROMIS Emotional Distress: Depressive symptoms SF (0.97) ²⁷ Daily pain severity rating; daily pain type rating # days recorded symptoms; # days and types of recorded treatments; # scheduled clinic appointments attended; # days daily mediation administered; # days PRN medications administered	meeting with mentor, clinic staff, and research team; baseline, mid-intervention, post-intervention, 3-months post-intervention
Adoption: Adherence Acceptability Education Symptom monitoring and tracking Patient-provider communication	# days symptoms recorded; # times educational component accessed; length of time in minutes educational component accessed; # text messages and videoconferences with nurse Caregiver satisfaction; # problems reported; types of problems reported # times accessed educational materials; length of time in minutes educational materials accessed # days recorded symptoms; # contacts (text or videoconferencing) with nurse pertaining to symptoms # and type (screening, referring, coaching, supporting) of contacts (text or videoconferencing) with nurse Collaborate for Parents	Tracking forms; content analysis from text messages and videoconferences with nurse, data transmitted from web-based application; fidelity checklist; weekly meetings with mentor and research team; caregiver interview at end of study
Implementation: Technology Consistency of intervention	# problems encountered with mobile device, # problems reported to research staff; types of problems reported instructional session conducted as planned; fidelity to protocol maintained MAPS	Tracking forms; weekly meeting with mentor and research team; caregiver interview at end of study
Maintenance: Projection of future adoption	# caregivers who would continue intervention; caregiver perception of the intervention; feasibility of nurse role	Caregiver interview at end of study; weekly meetings with mentor, clinic staff, and team

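### The 0-7 protocol models daily pain ratings in children from birth to age 7 with no age term, so comparisons of education dose between children can be confounded by age.

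*Combined protocol and SAP*

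**What the plan says.** All references are to the 0-7 years protocol unless stated.

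- **Population (Section 5.0).** The inclusion criterion is "Children ages 0 – 7 years and parent or primary caregiver 18 years of age or older", so there is no lower age limit.
- **Who reports (Section 5.0).** The rule is "Proxy data will be collected on children younger than 5 years, and older children (ages 5-7 years) without developmental delay will be invited". The invitation is for surveys and interviews, and the rule does not mention the daily app entries.
- **Scales with age floors (Section 3.0, measures table).** Parent-proxy pain interference applies from age 5 and the two PedsQL scales from age 2. Child pain, fatigue and quality of life are headed as proxy outcomes.
- **Daily ratings (same table).** "Daily pain severity rating; daily pain type rating" appears with no age range, scale, categories or named rater.
- **How pain is entered (Section 10.0).** The app is on the caregiver's device. It offers a "customizable avatar on which the user can record the location, severity, and characteristics of pain". The user is not identified as caregiver or child.
- **Model (Section 12.0).** Repeated measures ANCOVA is planned with "symptom (pain) severity and type obtained daily as dependent variable in individual models". Dose is the "number of times education module was accessed and total time spent in education modules". No other covariate is named.

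The model sentence is the same in the 8-17 protocol. There the app is on both the child's and the caregiver's devices (Section 10.0), and the youngest child is 8.

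**The concern.** The protocol accepts elsewhere that age governs how a child's symptoms can be measured: it sets floors on its proxy scales and a starting age for self-report. The daily ratings that carry the preliminary-effects model have no such rule, and the model has no term to absorb age differences. A caregiver's rating for an infant must rest on what the caregiver observes. For a six-year-old, it can also draw on what the child says. The same recorded score may then not mean the same thing across the age range.

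This matters most for the dose term. Section 1.0 says that caregivers of young children are often new to the disease, so their use of the education module may well differ from that of caregivers of older children. If both the rating and the dose shift with age, an apparent dose effect could be an age effect. For pain type, which the protocol does not define, one pooled result across all ages would be hard to interpret.

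**Working it through.** No figure in the plan depends on this point, so there is none to reproduce. The check is a short argument about the model, followed by an illustration of how the sample might divide by age.

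**1. Where age enters.** Write the rating for child i on day t as

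Y(i,t) = pain(i,t) + o(i),

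where o(i) is a rating offset that depends on the child's age.

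- *Within a child:* Y(i,t2) − Y(i,t1) = pain(i,t2) − pain(i,t1). A stable offset cancels, provided the model has a child effect. Section 12.0 does not say whether it has.
- *Between children:* Y(i) − Y(j) keeps o(i) − o(j). It does not cancel.

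Section 12.0 defines dose by an access count and a total time. If these are one value per child, which the plan does not state, the dose coefficient compares different children. With age left out, and other things equal, its bias is

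(effect of age on the rating at a given dose) × (slope of age on dose).

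The bias is zero if either factor is zero. The documents give neither factor, so its size and direction are unknown.

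**2. How the sample might divide.** Inputs: 30 dyads (Section 6.0) and drop-out of up to 30% (Section 12.0), which leaves 30 × 0.7 = 21. The documents give no age distribution. *Assumption:* ages are spread evenly over the eight single years 0 to 7. The bands follow the protocol's own cut-points at 2 and 5. Ranges are binomial 95% ranges.

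| Baseline age | Share | Of 30 (range) | Of 21 (range) |
|---|---|---|---|
| 0-1 | 2/8 | 7.5 (3-12) | 5.25 (2-9) |
| 2-4 | 3/8 | 11.25 (6-17) | 7.9 (4-12) |
| 5-7 | 3/8 | 11.25 (6-17) | 7.9 (4-12) |

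Under this assumption 30 × 5/8 = 18.75 children (range 13-24) are below 5, the age at which self-report begins. A clinic sample could be older or younger than this.

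**3. What the bands can support.** The 95% half-width for a mean, in SD units, is t(0.975, n−1)/√n:

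- n = 30: 0.37; n = 21: 0.46 (all children)
- n = 11: 0.67; n = 8: 0.84 (5-7 band)

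Results by band can only be descriptive. A covariate uses far less information: 1 degree of freedom for continuous age, or 2 for three bands.

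**The case against.** The other side has a good case against several stronger readings.

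- **A reader might infer that a caregiver cannot observe pain type in a pre-verbal child.** The documents do not say so, and they leave type undefined. If it includes location or another visible feature, a caregiver could record part of it.
- **A reader might infer that the model mixes child reporters with caregiver reporters.** This is not shown. The app is held by the caregiver and child outcomes are headed as proxy, so every daily rating may come from the caregiver. The self-report rule from age 5 concerns surveys and interviews.
- **A reader might infer that the daily ratings are the only pain measure below age 5.** This is unproven for ages 2-4. The PedsQL Sickle Cell Disease Module applies from age 2, and the documents do not set out its content.
- **A reader might conclude that pain type should be dropped below age 5.** That is a debatable trade-off. A feasibility study may want to know what caregivers of infants manage to record, and the number of children affected rests on an assumed age spread.

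Two further objections carry weight. Pooling all ages is inferred from the absence of any restriction; Section 12.0 does not state it. The analysis is also secondary, and the study disclaims any aim to confirm or refute hypotheses.

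These points narrow the concern and lower its severity. They do not supply an age term. Even with one rater throughout, what that rater can go on changes with the child's age, and the cancellation within a child does not protect comparisons between children.

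**Conclusion.** The concern holds in a limited form. As written, Section 12.0 of the 0-7 protocol adjusts the daily pain models for education dose alone, in children from birth to 7. Comparisons of dose between children are therefore open to confounding by age, and a single pooled result for pain type has no clear meaning across that range. Within-child change is much less exposed.

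This rests on two plausible conditions that the documents do not establish: that the meaning of the rating differs with age, and that education use does too. The size of any bias cannot be computed. The age-band counts illustrate an even spread of ages and do not predict the sample. Severity is low: no primary feasibility result depends on these models.

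**What to change.** In Section 12.0 of the 0-7 protocol:

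1. Add baseline age as a covariate in the daily severity model, either continuous or in bands 0-1, 2-4 and 5-7.
2. Label the daily ratings caregiver-reported, in line with the caregiver-held app and the proxy heading in the measures table.
3. Summarise pain type descriptively by age band, and do not interpret one pooled type result.

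Child age is already collected at baseline (Section 3.0, measures table), so this is a change of wording with no new data. The cost is 1 degree of freedom for continuous age or 2 for three bands, with 21 to 30 children. The bands will be small, and their summaries should be presented as descriptive. An age term does not remove every difficulty: the education materials include one on monitoring pain (Section 3.0), so dose could also change how caregivers rate. That caveat should accompany any dose result.
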